1 PROTOCOL SUMMARY

1.1 SYNOPSIS

Title:	A study to assess Midline Frontal Theta (MFT) power as measured by stimulus-locked electroencephalography (EEG) before and after AKL-T01 treatment for improving attention in pediatric participants ages 8-12 years old with Attention Deficit Hyperactivity Disorder (ADHD)
Hypothesis:	ADHD children receiving 4 weeks of AKL-T01 treatment will show enhancement in MFT activity as measured by stimulus-locked EEG.
Objectives:	
Primary Objective:
 
• Demonstrate enhancement of MFT power measured by stimulus-locked EEG (Perceptual Discrimination Task (PDT)=Stimulus) in children with ADHD following 4 weeks of at-home AKL-T01 treatment. 
Secondary Objective:
 
• Demonstrate normalized MFT power in children with ADHD following 4 weeks of at-home AKL-T01 treatment. 
Exploratory Objectives:
 
• Demonstrate improvement in sustained attention by direct assessment in children with ADHD following 4 weeks of at-home AKL-T01 treatment.• Demonstrate improvement in ADHD symptoms by parent report in children with ADHD following 4 weeks of at-home AKL-T01 treatment.
Endpoints:	
Primary Endpoint:
 
• PDT-locked EEG relative to pre-training 
Secondary Endpoint:
 
• PDT-locked EEG relative to a normative control cohort 
Exploratory Endpoints:
 
• Project EVO Assessment• Test of Variables of Attention (TOVA)• Vanderbilt Assessment
Study Population:	30 children ages 8 to 12 with ADHD from the United States
Description of Study Intervention:	AKL-T01 is a digital therapeutic software for the treatment of attention and inhibitory control deficits in patients with ADHD. AKL-T01 is an investigational medical device known as Software as a Medical Device (SaMD).
Study Duration:	From beginning of enrollment to last subject last visit, 12 months
Participant Duration:	29 Days

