4 STUDY DESIGN

4.1 OVERALL DESIGN

This study is a single arm, open-label, pilot study to assess midline frontal theta (MFT) power as measured by stimulus-locked electroencephalogram (EEG) before and after treatment with AKL-T01 for improving attention in pediatric participants ages 8-12 years old with attention deficit hyperactivity disorder (ADHD).

All participants enrolled in this study will not be taking ADHD medications, including stimulants, for the duration of the study. Participants who are taking ADHD medications prior to Day 0 must have been stable off of medications for at least 30 days per parent report, or washout of medications at a Screening visit 3 – 7 days prior to Day 0.

At Baseline / Day 0, all eligible participants will complete both resting-state and PDT-locked EEG, as well as the TOVA, Vanderbilt, and AKL-M01 assessments.

All participants will then play AKL-T01 for approximately 25 minutes per day, 5 days per week, for 4 weeks at home.

At Follow-up / Day 28, participants will repeat both resting-state and PDT-locked EEG, as well as the TOVA, Vanderbilt, and AKL-M01 assessments.

All study visits for each participant should be completed during the same time of day (either AM or PM), to maintain consistent data collection and comparison of rater assessment results.

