5 STUDY POPULATION

5.1 INCLUSION CRITERIA

In order to be eligible to participate in this study, an individual must meet all of the following criteria:

1. Age 8 to 12 at the time of parental informed consent
2. Male or female
3. Confirmed ADHD diagnosis at screening/baseline visit based on DSM-V criteria and established via the MINI-KID administered by a trained clinician either in person or via teleconference
4. WISC V FSIQ ≥ 70
5. Vanderbilt ADHD Diagnostic Parent Rating Scale: Must score a 2 or 3 on at least 6 items 1-9 AND must score a 4 on at least 2, or 5 on at least 1, of items 48-54 (performance questions).
6. Consistently off stimulant medication for ≥ 1 week. OR currently on stimulant medication and agree to stop taking the medication for a 1 week prior to the baseline visit and off through duration of training and post-training assessment (note: participants will only be allowed to washout of stimulant medication if in the opinion of the investigator they are currently inadequately managed on their medication and it is appropriate to stop taking their medication for the duration of the trial)
7. Consistently off Psychotropic drug for ≥ 1 month
8. Consistently off non-stimulant medication for ADHD (e.g. atomoxetine, clonidine, guanfacine) for ≥ 1 month

9. Able to follow written and verbal instructions (English) as assessed by the PI and/or study coordinator
10. Functioning at an age-appropriate level intellectually
11. Able to comply with all testing and requirements

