8 STUDY ASSESSMENTS AND PROCEDURES

8.1 ELIGIBILITY AND EFFICACY ASSESSMENTS

The following assessments will be administered to each eligible participant

Assessment	Purpose	Time to Administer
Eligibility		
MINI-KID	Confirm diagnosis of ADHD and identify any excluding comorbid diagnoses	20 minutes
WISC V	Determine IQ	60 minutes
Ishihara Colorblindness Test	Determine colorblindness	5 minutes
Efficacy		

Assessment	Purpose	Time to Administer
Vanderbilt ADHD Diagnostic Parent Rating Scale	Assess severity of ADHD symptoms and effect on behavior.	20 minutes
Resting State EEG	Assess MFT activity in a resting state	6 min
PDT-locked EEG	Assess MFT activity during a Perceptual Discrimination Task	1 hour
Test of Variables of Attention (TOVA)	Assess objective attention	22 minutes
AKL-M01 (EVO Monitor)	Assess MFT activity during a AKL-M01 session	20 minutes

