8.2 SAFETY AND OTHER ASSESSMENTS

Safety assessments will include the evaluation of adverse device effects (ADEs).

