8.3.5 TIME PERIOD AND FREQUENCY FOR EVENT ASSESSMENT AND FOLLOW-UP

The occurrence of an ADE may come to the attention of study personnel during study visits and interviews of a study participant presenting for medical care, or upon review by a study monitor.

Information to be collected includes event description, time of onset, clinician's assessment of severity, relationship to study product (assessed only by those with the training and authority to make a diagnosis), and time of resolution/stabilization of the event. All ADEs occurring while on study will be documented appropriately regardless of relationship. All ADEs will be followed to adequate resolution.

Any medical condition that is present at the time that the participant is screened will be considered as baseline and not reported as an ADE. However, if the study participant's condition deteriorates at any time during the study, it will be recorded as an ADE.

Changes in the severity of an ADE will be documented to allow an assessment of the duration of the event at each level of severity to be performed. ADEs characterized as intermittent require documentation of onset and duration of each episode.

The Site Principal Investigator will record all reportable events with start dates occurring from the time of enrollment through the final study visit. At each study visit, the investigator will inquire about the occurrence of ADEs since the last visit. Events will be followed for outcome information until resolution or stabilization.

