9.3 STATISTICAL ANALYSES

All statistical analyses will be conducted using SPSS 22.0 (SPSS Inc.). Group effects for both behavioral and neural measures will be assessed with separate ANOVAs and ANCOVAs with planned follow-up contrasts (Fisher's LSD). The ANCOVA approach is considered to be a more suitable approach when post-test performance that is not conditional / predictable based on pre-test performance is the primary outcome of interest following treatment, as opposed to characterizing gains achieved from pre-training performance (for example, group X session interaction(s)). However, both are appropriate statistical approaches that have been used to assess cognitive training outcomes. Thus, our approach will be to present the p-values for each approach. Planned follow-up contrasts will be used to directly assess changes within each group. To minimize influential data points, we will remove values +/- 2 standard deviations for all group analyses. For correlations tested, we will use a more stringent outlier removal procedure (Cook's D> 1) given the smaller cohort size and possible inflated change scores.

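### The only ADHD-symptom rating repeated after baseline is used at follow-up solely in a trimmed, completer-filtered group analysis of improvement, which biases the mean toward improvement if a minority worsens

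*Combined protocol and SAP*

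**What the plan says.** **Population.** The Synopsis plans "30 children ages 8 to 12 with ADHD from the United States" in a single arm. Section 4.1 states: "All participants enrolled in this study will not be taking ADHD medications, including stimulants, for the duration of the study". Criterion 6 of section 5.1 lets some children stop stimulants in order to enter and keeps them "off through duration of training and post-training assessment".

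**The measure.** The schedule in 1.3 and section 4.1 place the parent Vanderbilt at Day 0 and Day 28. MINI-KID and BASC-2 are baseline only. TOVA and AKL-M01 are repeated but are performance tests, and the Social Competence Scale is repeated but does not rate ADHD symptoms. The Vanderbilt is therefore the only ADHD-symptom rating after baseline.

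**Its planned use.** Apart from eligibility (5.1, criterion 5), the Synopsis ties parent report to one exploratory aim, "Demonstrate improvement in ADHD symptoms by parent report in children with ADHD". Section 8.1 lists the scale under Efficacy, with the purpose "Assess severity of ADHD symptoms and effect on behavior". The endpoint table in section 3 does not list it.

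**Its analysis.** Section 9.3 plans ANOVAs and ANCOVAs of group effects for behavioral and neural measures, and adds "we will remove values +/- 2 standard deviations for all group analyses". It does not say whether this applies to raw or change scores, and plans no analysis without removal. Section 9.2 limits the analysis to children who complete half or more of the treatment.

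**Deterioration.** Section 8.2 names only ADEs as safety data. Section 8.3.5 says that if a participant's "condition deteriorates at any time during the study, it will be recorded as an ADE", and has the investigator ask about ADEs at visits. It names no instrument, comparison or threshold.

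**The concern.** ADHD is present at screening in every child, so worsening of ADHD falls within the wording of 8.3.5. The one scale that would show it is collected at both visits, in children who are all unmedicated. Its planned follow-up use looks only for improvement in a group mean, after two exclusions that can each remove children who do badly.

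- **The 2 SD rule.** It is symmetric in form but need not be in effect. If most children improve and a few worsen, the few sit in the far tail of the change distribution and are more likely to be cut.
- **The 50% filter.** It leaves out children who stop early. Section 7.1.1 allows withdrawal for disease progression, and the schedule has no Vanderbilt at early exit, so a child who worsens and stops may leave no follow-up score.

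At stake is whether a reader of the results could see that some children got worse while the reported mean improved. No planned table shows individual change.

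**Working it through.** The plan states no SD, effect size, power or error rate for the Vanderbilt, so there is no figure of its own to reproduce. Everything below rests on assumptions: 9.3 covers the Vanderbilt as a behavioral measure, removal is a single pass on change scores at the sample mean ± 2 sample SD, and n = 30.

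**1. No distinct group of worseners (normal changes).**
- Share removed: 2 × (1 − Φ(2)) = 4.55%. Expected removals: 30 × 0.0455 = 1.37, of which 0.68 on the worsening side.
- Chance of at least one removal on that side: 1 − (1 − 0.02275)^30 = 50%.
- Removal is about equal on the two sides, so there is no systematic shift of the mean.

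**2. A minority worsens.** Positive means improvement. Worseners have a true change of −1.0 SD, the others +0.5 to +1.0 SD, with within-class SD 0.7. The test is a two-sided one-sample t-test at 0.05, counted when it shows improvement; for two visits it equals the repeated-measures ANOVA test of session. There were 20,000 simulated trials per setting.

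| True worseners | Worseners deleted | Improvement declared, all data | Improvement declared, after removal |
|---|---|---|---|
| 3 of 30 | 32% to 48% | 61% to 99.9% | 81% to over 99.9% |
| 6 of 30 | 16% to 21% | 14% to 93% | 37% to 98% |

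With 3 worseners, 1% to 2% of improvers are deleted. The lower declared rates belong to an improvement of 0.5 SD in the others. There the true mean changes are (27 × 0.5 − 3 × 1)/30 = 0.35 and (24 × 0.5 − 6 × 1)/30 = 0.20 SD.

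**3. A second model gives the same direction.** Here positive means worse. The other children follow N(−0.5, 1) and k children are centred on a worsening of 3 SD.

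| k of 30 | Worseners deleted | Mean, all data | Mean after removal |
|---|---|---|---|
| 1 | 90% | −0.38 | −0.48 |
| 2 | 77% | −0.27 | −0.45 |
| 3 | 62% | −0.15 | −0.39 |
| 5 | 34% | +0.08 | −0.15 |

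At k = 5 the mean changes sign. At k = 8 only 11% of worseners are deleted.

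**4. Why deletion fades as worseners multiply.** If k children worsen equally and the rest are equal, their standardised distance is z = √[((n − k)/k) × ((n − 1)/n)].
- k = 5: √(5 × 29/30) = 2.20, beyond the cut.
- k = 6: √(4 × 29/30) = 1.97, inside it.

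**5. What a raw count of any worsening would show.** Under the model in step 2, with no true worseners and a mean improvement of 0.5 SD, the expected count is 30 × Φ(−0.5/0.7) = 30 × 0.2375 = 7.1. With 3 true worseners it is 27 × 0.2375 + 3 × Φ(1/0.7) = 6.4 + 2.8 = 9.2, and most of those counted belong to the improving class.

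**The case against.** **ADE recording is separate.** A reader might infer that a child trimmed under 9.3 is lost as an ADE. The documents do not support that. Removal applies to group analyses; 8.3.5 has the investigator ask about and record events, and 8.3.6 requires all ADEs to be reported within 24 hours. A child can be trimmed from an ANOVA and still be recorded. What remains is that nothing connects the Day 28 score to that judgement.

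**Most worseners are not deleted.** A reader might also infer that the rule picks out precisely the children who worsened. In step 2 at least half of them stay in and are averaged, and large improvers can be cut too. The single worst child is deleted in 81% to 94% of trials with 3 worseners, but the lowest of 30 values is deleted in about 52% of trials with no worsened class at all. The imbalance between worseners and improvers is what stands.

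**Any mean can improve while a minority worsens.** True: with 3 worseners and all data kept, improvement is already declared in 61% to 99.9% of trials. The part due to the rule is the increase, which is largest where average improvement is modest.

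**A count of worsened children is mostly noise.** This stands (step 5). An observed 6 of 30, with exact 95% interval 8% to 39%, is compatible with no true worsening, because the interval covers sampling error and not misclassification.

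**Stopping stimulants.** Day 0 is already off drug for washout children, so the change score cannot show the effect of stopping. This stands too.

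**Risk/benefit.** The favorable statement in 2.3.3 rests on earlier studies, so this trial's Vanderbilt analysis does not undermine it.

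**Conclusion.** The concern holds as a reporting and bias problem in an exploratory measure. The only follow-up rating of ADHD symptoms in unmedicated children has one planned use, a group analysis of improvement, and the removal rule biases that analysis toward improvement when a minority worsens and most improve. In the illustration, the chance of declaring improvement rises from 14% to 37% with 6 of 30 worsening and the rest improving by 0.5 SD. With 3 of 30 worsening, 32% to 48% of worseners are deleted against 1% to 2% of improvers.

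These sizes depend on assumed SDs, the assumed mixture and removal on change scores. If changes are near normal with no distinct worsened group, removal is roughly balanced. The effect of the 50% filter cannot be sized from the documents.

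The documents do not show that recorded harm would be erased. They show a missing link between the Vanderbilt and 8.3.5, and an unclear place for worsening while off medication: 8.3.1 limits ADEs to device-related events, whereas 8.3.5 records deterioration as an ADE and documents ADEs whatever their relationship.

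**What to change.** **Section 9.3.**
- Report the Day 0 to Day 28 Vanderbilt change for every treated child with a Day 28 score, without the 2 SD removal and without the 50% filter.
- Show it as an individual listing or plot with the untrimmed mean and confidence interval, overall and by whether the child stopped stimulants to enter.
- State that Day 0 is already off drug for washout children, so the change covers the treatment period only.
- If a count of worsened children is given, label it descriptive. Say that, without a control arm, a count of any worsening is largely measurement noise (about 7 of 30 expected with no true worseners, under the assumed SD and a 0.5 SD mean improvement). Any deterioration threshold is for the sponsor and investigators to set.

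**Section 8.3.** Make each child's Day 0 and Day 28 scores available to the investigator for the 8.3.5 judgement. Reconcile 8.3.1 with 8.3.5 so that it is clear where worsening not attributed to the device is recorded.

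**Cost.** A few sentences and one extra table or plot from data already collected. The downside is that a less favourable figure may appear beside the planned mean.

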8.3.6 ADVERSE EVENT REPORTING

It is understood that complete information about an event may not be known at the time the initial report is submitted. The investigator must assess the relationship of the event to the investigational device (including rationale for assessment) and should make every attempt to obtain as much information as possible concerning the event. Additional information pertaining to an event should be reported in the case report form as it becomes available.

The investigator must report all adverse device effects (anticipated or unanticipated) occurring from the time of enrollment through the final study visit within 24 hours of knowledge of the event.

The investigator must report when important follow-up information (final diagnosis, outcome, results of specific investigations, etc.) becomes available after submission of the initial ADE form and information. Follow-up information should be submitted according to the same process used for reporting the initial event as described above (i.e., within 24 hours of knowledge, via <specify method>). All adverse device effects will be followed through resolution.

8.4 UNANTICIPATED PROBLEMS

8.4.1 DEFINITION OF UNANTICIPATED PROBLEMS (UP)

The Office for Human Research Protections (OHRP) considers unanticipated problems involving risks to participants or others to include, in general, any incident, experience, or outcome that meets all of the following criteria:

- Unexpected in terms of nature, severity, or frequency given (a) the research procedures that are described in the protocol-related documents, such as the Institutional Review Board (IRB)-approved research protocol and informed consent document; and (b) the characteristics of the participant population being studied;
- Related or possibly related to participation in the research (“possibly related” means there is a reasonable possibility that the incident, experience, or outcome may have been caused by the procedures involved in the research); and
- Suggests that the research places participants or others at a greater risk of harm (including physical, psychological, economic, or social harm) than was previously known or recognized.

In addition, UPs include unanticipated adverse device effect, any serious adverse effect on health or safety, or any life-threatening problem or death caused by, or associated with, a device, if that effect, problem, or death was not previously identified in nature, severity, or degree of incidence in the investigational plan or application (including a supplementary plan or application), or any other unanticipated serious problem associated with a device that relates to the rights, safety, or welfare of subjects (21 CFR 812.3(s)).

- Examples of potential UPs include but are not limited to:
 1. Unanticipated misuse of device hardware
 2. Unanticipated misuse of device software
 3. Unanticipated hardware issues
 4. Unanticipated software issues

8.4.2 UNANTICIPATED PROBLEM REPORTING

The investigator will report unanticipated problems (UPs) to the reviewing Institutional Review Board (IRB) and to the Data Coordinating Center (DCC)/lead principal investigator (PI). The UP report will include the following information:

- Protocol identifying information: protocol title and number, PI's name, and the IRB project number;
- A detailed description of the event, incident, experience, or outcome;
- An explanation of the basis for determining that the event, incident, experience, or outcome represents an UP;
- A description of any changes to the protocol or other corrective actions that have been taken or are proposed in response to the UP.

An investigator shall submit to the sponsor and to the reviewing Institutional Review Board (IRB) a report of any unanticipated adverse device effect occurring during an investigation as soon as possible, but in no event later than 10 working days after the investigator first learns of the effect (21 CFR 812.150(a)(1)). A sponsor who conducts an evaluation of an unanticipated adverse device effect under 812.46(b) shall report the results of such evaluation to the Food and Drug Administration (FDA) and to all reviewing IRBs and participating investigators within 10 working days after the sponsor first receives

notice of the effect. Thereafter the sponsor shall submit such additional reports concerning the effect as FDA requests (21 CFR 812.150(b)(1)).

9 STATISTICAL CONSIDERATIONS

9.1 STATISTICAL HYPOTHESES

OBJECTIVE	HYPOTHESIS
Primary	Children with ADHD, following 4 weeks of digital treatment with AKL-T01, will demonstrate enhancement of MFT power as measured by stimulus-locked EEG.
Secondary	Children with ADHD, following 4 weeks of digital treatment with AKL-T01, will demonstrate normalized MFT power as compared with a neurotypical population.

9.2 POPULATIONS FOR ANALYSES

There will be two populations for analysis in this study.

The AKL-T01 Intervention Population will complete 28 days of AKL-T01 digital treatment. This population will enroll pediatric ADHD participants according to the inclusion criteria outlined in section 5.1 of this protocol. Only participants completing at least 50% of the prescribed treatment (i.e. 50 sessions) will be included in the analysis.

The neurotypical control group will also be analyzed as historical controls. This population was enrolled in *A pilot study to determine the feasibility of enhancing cognitive abilities in children with sensory processing dysfunction* (Anguera, 2017).

9.3 STATISTICAL ANALYSES

All statistical analyses will be conducted using SPSS 22.0 (SPSS Inc.). Group effects for both behavioral and neural measures will be assessed with separate ANOVAs and ANCOVAs with planned follow-up contrasts (Fisher's LSD). The ANCOVA approach is considered to be a more suitable approach when post-test performance that is not conditional / predictable based on pre-test performance is the primary outcome of interest following treatment, as opposed to characterizing gains achieved from pre-training performance (for example, group X session interaction(s)). However, both are appropriate statistical approaches that have been used to assess cognitive training outcomes. Thus, our approach will be to present the p-values for each approach. Planned follow-up contrasts will be used to directly assess changes within each group. To minimize influential data points, we will remove values +/- 2 standard deviations for all group analyses. For correlations tested, we will use a more stringent outlier removal procedure (Cook's D> 1) given the smaller cohort size and possible inflated change scores.

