2 INTRODUCTION

2.1 BACKGROUND

Akili Interactive's videogame-like digital treatment, AKL-T01™ (EVO™-Multi), is based on the work of UCSF [name], MD, who has identified a way to measure and improve the ability to process interference events (essentially, interruptions and distractions). Interference susceptibility is recognized as a limiting factor across global executive function (including attention and memory) and is known to be fragile in multiple diseases. [name] work also demonstrated that changes in EEG signals occurred at neurological loci associated with cognitive control. The basic scientific mechanisms underlying AKL-T01 have been tested in controlled (N=203) studies of healthy participants across a wide age range (8 to 70 years of age) to validate the ability to detect differences between age groups and to enhance interference processing in older adults. AKL-T01 was tested in a, follow-on, controlled (N=80) study of ADHD children and age-matched neurotypical controls to validate its ability to detect differences between the groups and to provide insight into AKL-T01 as a therapeutic product. Findings provide preliminary support that this digital treatment may improve attention, working memory, and inhibition in children with ADHD. The pivotal study STARS-ADHD; a multi-center, randomized, double-blind, active-controlled study of AKL-T01 in 348 pediatric subjects ages 8-12 with ADHD demonstrated a statistically significant improvement ($p=0.006$) between AKL-T01 and an active control on the primary endpoint (TOVA API change from Baseline to Post-Treatment) (STARS-ADHD, in progress).

Most relevant to this protocol is a published feasibility study of pediatric Sensory Processing Dysfunction (SPD) at the University of California, San Francisco (UCSF), which requested that 57 children ages 8 to 12 (24 Neurotypical, 20 SPD with inattention, and 13 SPD without inattention) to engage with AKL-T01 treatment at home for 30 minutes per day, 5 days per week for 4 weeks. Participants were assessed using EEG, TOVA and the Vanderbilt Inattention scale (parent-reported) at Baseline/Day 0 and at Exit/Day 28. All children showed statistically significant improvement in attention as measured by TOVA. Children with SPD and with inattention also showed statistically significant enhancement of Mid-Frontal Cortex Theta power as measured by EEG while neurotypical and SPD children without inattention did not.

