3 OBJECTIVES AND ENDPOINTS

OBJECTIVES	ENDPOINTS
Primary	
Demonstrate enhancement of MFT power measured by stimulus-locked EEG (Perceptual Discrimination Task (PDT)=Stimulus) in children with ADHD following 4 weeks of at-home AKL-T01 treatment.	Change in midline frontal theta power as measured by PDT-locked EEG.
Secondary	
Demonstrate normalized MFT power in children with ADHD following 4 weeks of at-home AKL-T01 treatment.	MFT power of ADHD cohort at Day 28 compared to that of neurotypical cohort at Day 0 (historical controls).
Exploratory	
Demonstrate improvement in attention in children with ADHD following 4 weeks of at-home AKL-T01 treatment.	
Reaction time and reaction time variability as measured by TOVA.Reaction time and reaction time variability as measured by perceptual discrimination task.Reaction time and reaction time variability as measured by ALK-M01 Assessment.

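### Section 9.3 names no separate test for the primary ADHD pre-post MFT change; run as a Fisher's LSD contrast with the historical controls in the model, its standard error would rest on an unchecked equal-variance assumption.

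*Combined protocol and SAP*

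**What the plan says.** The design is one enrolled cohort: "This study is a single arm, open-label, pilot study to assess midline frontal theta (MFT) power" (section 4.1), with "30 children ages 8 to 12 with ADHD from the United States" (section 1.1). The primary endpoint is a change within that cohort: "Change in midline frontal theta power as measured by PDT-locked EEG" (section 3).

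Section 9.2 adds a second analysis population from the earlier feasibility study: "The neurotypical control group will also be analyzed as historical controls". It gives no number. Section 2.1 describes that study as "57 children ages 8 to 12 (24 Neurotypical, 20 SPD with inattention, and 13 SPD without inattention") and says its participants had EEG at Day 0 and Day 28.

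Section 9.3 is the only text on how change is tested. It plans ANOVAs and ANCOVAs for group effects, with "planned follow-up contrasts (Fisher's LSD"), and mentions the group by session interaction as an example of the gain-score approach. P-values from both approaches are to be presented. It then says: "Planned follow-up contrasts will be used to directly assess changes within each group". The same section removes values beyond 2 SD in all group analyses. It does not state the error term of the contrasts, which groups enter the model for the primary endpoint, or any check of variances.

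**The concern.** An LSD contrast takes its error term from the parent ANOVA. In a two-group by session ANOVA, the error for a within-group change is the change-score variance pooled over both groups. The precision of the ADHD change would then depend partly on children from another study without the diagnosis. Section 9.3 uses the same term for the LSD contrasts and for the contrasts that assess change within each group, and the only second group in the plan is the historical one. Pooling is therefore a natural reading of the text.

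At stake are the p-value and confidence interval for the primary question. If neurotypical change varies less than ADHD change, the test gives too many false positives. If it varies more, the test loses power.

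**Working it through.** **Nothing to reproduce.** The documents give no alpha, power, SD, effect size or sample-size calculation.

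**Inputs**
- ADHD children: 30 (section 1.1). The 50% completion rule in section 9.2 may lower the analysed number.
- Neurotypical children: 24 (section 2.1). It is an assumption that all 24 are used, and with both visits.
- Test: two-sided at 5% (assumed).
- r = neurotypical SD of change / ADHD SD of change: assumed, 0.5 to 2.
- Normal data, with no outlier removal.

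**Error term.** Let s1 and s2 be the SDs of the Day 28 minus Day 0 change in ADHD and neurotypical children. In the group by session ANOVA:

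2 × within-subject MSE = (29·s1² + 23·s2²)/52

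This was checked by fitting the model to one simulated data set with 30 and 24 children. Both sides equalled 1.2829 on 52 df. The contrast SE was √(1.2829/30) = 0.207, against 0.253 from the ADHD children's own changes.

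**SE ratio.** The LSD contrast uses √(2·MSE/30). The ADHD children's own SE is s1/√30. The ratio is √((29 + 23r²)/52). At r = 0.5 this is √(34.75/52) = 0.82, and at r = 1.5 it is √(80.75/52) = 1.25.

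**Type I error.** This was simulated with 1,000,000 runs per setting, comparing the pooled contrast (52 df, critical t 2.007) with a paired t-test in ADHD children alone (29 df, critical t 2.045). Separate runs agree to about 0.1 percentage point.

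| r | SE used / own SE | Pooled contrast | Paired test, ADHD only |
|---|---|---|---|
| 0.5 | 0.82 | 10.8% | 5.0% |
| 0.8 | 0.92 | 7.2% | 5.0% |
| 1.0 | 1.00 | 5.0% | 5.0% |
| 1.25 | 1.12 | 2.9% | 5.0% |
| 1.5 | 1.25 | 1.6% | 5.0% |
| 2.0 | 1.53 | 0.4% | 5.0% |

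With only 20 analysable ADHD children, the pooled contrast gives 13.2% at r = 0.5 and about 0.25% at r = 2.

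**Cost of not pooling when r = 1.** At an assumed true change of 0.5 SD, power is 76.6% pooled and 75.4% paired, a difference of 1.2 percentage points.

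**Effect of the 2 SD rule on the paired test.** With n = 30 normal change scores and one pass of removal beyond 2 SD, type I error of the paired t-test is about 10%. With removal at each session and loss of the pair, it is 6.5% to 8.5% for an assumed pre-post correlation of 0.7 to 0.3. The 5.0% column above therefore holds only without removal.

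**The case against.** The strongest reply is that the plan never says it pools. LSD is attached to the ANOVAs and ANCOVAs for group effects, and the sentence on change within each group gives no error term. Section 3 uses the neurotypical cohort at Day 0 only, and only for the secondary endpoint. If that is all they contribute, no group by session model can be fitted to them and the fault cannot arise. This stands, so the point is conditional. Against it, change within each group needs two visits per group, section 2.1 shows that Day 28 EEG was recorded in that study, and no ADHD-only test is described. Sections 3 and 9.3 do not settle the matter.

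A reader might infer unequal variances from the background, where inattentive children with sensory processing dysfunction showed significant "enhancement of Mid-Frontal Cortex Theta power as measured by EEG while neurotypical and SPD children without inattention did not". That does not follow. A pattern of significance carries no SD and says nothing about a variance ratio or its direction, and those inattentive children were not a confirmed ADHD cohort.

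Equal variance is also an ordinary ANOVA assumption, and pooling gains degrees of freedom when it holds. That is true, but the gain here is about 1 percentage point of power.

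Finally, the ANCOVA route (Day 28 adjusted for Day 0) compares groups and is not affected. It also does not test the ADHD pre-post change, so it cannot take the place of the contrast.

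**Conclusion.** The point holds in conditional form. Section 9.3 leaves the primary test and its error term unstated. Its text, run as written with the historical children in a group by session ANOVA, gives a standard error that is right only under equal change variances. Under the stated assumptions (30 and 24 children, normal data, no outlier removal), two-sided type I error would run from about 10.8% at an SD ratio of 0.5 to 1.6% at 1.5, with no error at 1.0.

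A reader might go further and conclude that the primary result will have wrong error bars or an inflated false-positive rate. The documents do not support that: pooling is an inference, and neither the size nor the direction of any error can be shown without SDs. For a single-arm pilot this is a should-fix, not a must-fix.

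**What to change.** In section 9.3, state that the primary test is the Day 28 minus Day 0 change in MFT power in ADHD children, by paired t-test with a 95% CI. It should use only those children's change SD (df = n − 1), with no historical child in the error term. Use Fisher's LSD contrasts only for between-group comparisons.

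State also that the 2 SD removal rule does not apply to this primary test. Otherwise the paired test would itself miss its 5% level.

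The cost is protocol wording. With 30 ADHD children, error df falls from 52 to 29 and critical t rises from 2.01 to 2.05, about 1 percentage point of power if the variances are in fact equal. In return, the primary p-value and interval no longer depend on the variability of another study's children.
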